Descriptive statistics will be displayed to provide an overview of the study results. For categorical variables, the number and percentage of subjects in each category will be presented. The denominator for percentages will be based on the number of subjects included in the respective analysis set. For observed case (OC) summaries, or summaries of data where no imputation is made for missing data, subjects with missing data will be accounted for by including a “Missing” category (corresponding to subjects with missing data for the variable being summarized) as the last row in the list of categories being summarized. Percentages will be presented to 1 decimal place. If the percentage is 100%, no decimal will be presented. If the percentage is 0, no percentage will be presented. The % sign will be presented in the column header, but not with each individual value.

For continuous variables, descriptive statistics will include number of subjects with available measurements (n), mean, standard deviation (SD), median, minimum, and maximum. Decimal places for descriptive statistics will apply the following rules:

- “n” will be an integer.
- Arithmetic and geometric mean, SD, and median will use 1 additional decimal place compared to the original data.

- Coefficient of variation (CV [%]) will be presented with 1 decimal place.
- Minimum and maximum will have the same number of decimal places as the original value.

The number of decimal places used for derived efficacy variables is shown in [Table 3-1](#).

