#### 3.10.1 Changes related to COVID-19

The impact of the COVID-19 pandemic on study procedures/conduct and on the primary safety endpoints (TEAEs, serious TEAEs, and study withdrawal due to TEAEs) will be investigated and additional outputs provided as appropriate. These analyses were not planned as part of the protocol as the pandemic was not ongoing at the time of protocol finalization.

The additional analyses are described in the following sections of the SAP:

- Subject disposition, including details of impacted visits and effects on collection and reporting of efficacy data ([Section 5.1.1](#))
- Adverse events ([Section 10.2.4](#))

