### **5 STUDY POPULATION CHARACTERISTICS**

#### **5.1 Subject disposition**

Subject disposition (date of first and last subject visit, number of subjects included in each analysis set [ES, SS, and FAS]) will be presented overall, by region and for each site, and by treatment group at completion of PA0008 and overall for the ES.

The number and percentage of subjects in each analysis set (ES, SS and SS Sub-populations, and FAS) will be presented by treatment group at completion of PA0008 and overall.

The number and percentage of subjects who started, completed and discontinued the study, along with the primary reason for discontinuation will be presented by treatment group at completion of PA0008 and overall for the SS (a subject will be considered to have completed the study if they attended Visit 13 [Week 104]). For the purposes of the summaries the data will be taken directly from the eCRF page for study termination.

The number and percentage of subjects who started, completed and discontinued study medication, along with the primary reason for medication discontinuation will be presented by treatment group at completion of PA0008 and overall for the SS (a subject will be considered to have completed study treatment if they received a dose at Visit 12 [Week 100]). For the purposes of the summaries the data will be taken directly from the eCRF page for study medication discontinuation.

For any subjects where the data on the study termination and study medication discontinuation eCRF pages are inconsistent, the data reported on the study termination page will be considered

as primary ie, if a subject is reported as discontinuing from the study, they will be regarded as discontinuing study medication as well (regardless of whether this is reported in the eCRF).

Discontinuations due to AEs will be summarized by treatment group at completion of PA0008 and overall for the SS.

Subjects who did not meet the eligibility criteria and the inclusion and/or exclusion criteria not met will be listed for the ES.

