## 8.5 Impact of COVID-19

Additional sensitivity analyses as a result of the global COVID-19 pandemic are not anticipated as the onset of the pandemic was subsequent to all subjects completing Week 48; therefore, there is no impact on the analysis of the secondary efficacy endpoint.

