Summaries of AEs in PA0008 and PA0009 combined will include AEs with onset on the first dose of bimekizumab in PA0008 up to 140 days after the last dose of bimekizumab in PA0009. AEs which occur on the day of a treatment switch will be considered to have begun on the previous treatment, with the exception of the following AEs which will be considered to have begun on the new treatment:

- Events that fulfill the anaphylaxis criteria for acute events (see [Section 10.2.3](#)).
- Events that fulfill the hypersensitivity reaction criteria for (see [Section 10.2.3](#)).
- Events with a HLT of “Administration site reactions NEC”.
- Events with an HLT of “Injection site reactions”.

AEs that occur on the first day of bimekizumab treatment in PA0008 following initial treatment with placebo will not be included in the summaries, unless they fulfill 1 of the 4 exception criteria above. AEs that occur after the last dose of bimekizumab in PA0009 and up to 140 days after the last dose of bimekizumab in PA0009 will be assigned to bimekizumab 160mg.

AEs will be presented as “number of subjects (percentage of subjects) [number of events]”. “[number of events]” will include all cases of an AE including repeat occurrences in individual subjects, while “number of subjects” will count each subject only once.

An overview of TEAE (number and percentage of subjects with any TEAE, serious TEAE, TEAE leading to study discontinuation, TEAE leading to permanent withdrawal of study medication, drug-related TEAE, severe TEAE, fatal AE [see note below], fatal TEAE and TEAE

with missing seriousness) will be provided by treatment group at completion of PA0008 and overall. This summary will be repeated by SS Sub-population.

This table will be repeated including all TEAEs in PA0008 and PA0009 reported for subjects in the PA0009 SS (with the exception of those with onset during placebo treatment) combined. The 'BKZ 160mg' treatment column in this table will include subjects in both the BKZ 160mgLD and BKZ 160mg treatment groups.

The category for fatal AEs will be based on all subjects enrolled in PA0009 in all the above summaries.

The following categories of TEAE will be summarized by MedDRA SOC, HLT and PT including EAIR and EAER (calculated as described in [Section 10.2.2](#)), where all summaries refer to AEs reported in PA0009 only except where stated:

- All TEAEs by treatment group at completion of PA0008 and overall.

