#### 10.2.4 Impact of COVID-19

In order to assess the impact of the COVID-19 global pandemic on the primary safety endpoint of incidence of TEAEs and serious TEAEs, additional listings and summaries will be presented.

For reporting purposes AEs will be assigned to ‘Prior to COVID-19 pandemic’ or ‘During the COVID-19 pandemic’ based on the following:

- If the date of AE onset (based on imputed start date) is prior to 11 March 2020 the AE will be assigned as ‘Prior to COVID-19 pandemic’
- If the date of AE onset (based on imputed start date) on or after 11 March 2020 the AE will be assigned as ‘During the COVID-19 pandemic’
  - The date of 11 March 2020 is chosen as the date the World Health Organization declared COVID-19 as a pandemic.

A ‘Post the COVID-19 pandemic’ phase will not be assigned for AE reporting as the pandemic is expected to be ongoing at the time of last subject last visit.

The following categories of TEAE will be summarized by MedDRA SOC, HLT and PT, including EAIR and EAER:

- All TEAEs by time of onset relative to COVID-19 pandemic (‘Prior to COVID-19 pandemic’ and ‘During the COVID-19 pandemic’)
- All TEAEs by time of onset relative to COVID-19 pandemic (‘Prior to COVID-19 pandemic’ and ‘During the COVID-19 pandemic’) and by region
- All serious TEAEs by time of onset relative to COVID-19 pandemic (‘Prior to COVID-19 pandemic’ and ‘During the COVID-19 pandemic’)
- All serious TEAEs by time of onset relative to COVID-19 pandemic (‘Prior to COVID-19 pandemic’ and ‘During the COVID-19 pandemic’) and by region
- All COVID-19 related TEAEs by treatment at completion of PA0008 and overall
  - COVID-19 related TEAEs will be identified based on the verbatim term including the text string ‘COVID’. These will include confirmed or suspected COVID-19 infections.

- All COVID-19 related TEAEs by treatment at completion of PA0008 and overall, and by region

The following categories of TEAE will be summarized by MedDRA SOC, HLT and PT:

- TEAEs leading to study discontinuation and/or permanent withdrawal of study medication by time of onset relative to COVID-19 pandemic ('Prior to COVID-19 pandemic' and 'During the COVID-19 pandemic')
- TEAEs leading to study discontinuation and/or permanent withdrawal of study medication by time of onset relative to COVID-19 pandemic ('Prior to COVID-19 pandemic' and 'During the COVID-19 pandemic') and by region

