A separate listing of all COVID-19 related AEs will be presented, where COVID-related AEs are identified as described above. In addition, the time of onset of each AE relative to the COVID-19 pandemic will be flagged in all AE listings.

For the purpose of calculating EAIR and EAER prior to and during the COVID-19 pandemic the rules in [Table 10-5](#) will be applied in the calculation of exposure time at risk. An individual subject may therefore be counted in the denominator for both periods ('Prior to COVID-19 pandemic' and 'During the COVID-19 pandemic') dependent on whether the subject is still considered at risk on 11 March 2020. In this case time at risk will be calculated separately for each period. Subjects who have discontinued study medication prior to 11 March 2020 may be included in the denominator for the 'During the COVID-19 pandemic' period if they are still considered to be at risk following the last dose of study medication in the 'Prior to COVID-19 pandemic' period.

Subjects who are no longer in the exposure time at risk period ([Table 10-2](#)) on 11 March 2020, will not be counted in the denominator for the 'During the COVID-19 pandemic' period.

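### SAP 10.2.4 compares withdrawals due to TEAEs before and during COVID-19 by percentage alone, across windows of unequal length and with no period denominator

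*SAP*

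**What the plan says.** SAP 3.10.1 undertakes to investigate the impact of the pandemic on "TEAEs, serious TEAEs, and study withdrawal due to TEAEs". Withdrawal due to TEAEs is the secondary safety variable (SAP 2.2.1.2).

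SAP 10.2.4 assigns each event to a period by onset date, with the cut at 11 March 2020, and then gives two lists of tables.

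- The first list covers all TEAEs, serious TEAEs and COVID-19-related TEAEs. Its lead-in reads "The following categories of TEAE will be summarized by MedDRA SOC, HLT and PT, including EAIR and EAER".
- The second list has a lead-in that does not mention those rates. It holds "TEAEs leading to study discontinuation and/or permanent withdrawal of study medication by time of onset relative to COVID-19 pandemic", overall and by region.

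The default AE display in SAP 10.2 is "number of subjects (percentage of subjects) [number of events" (closing bracket omitted). SAP 3.1 states: "The denominator for percentages will be based on the number of subjects included in the respective analysis set". SAP 10.2.4 does give period denominators, including that "Subjects who have discontinued study medication prior to 11 March 2020 may be included in the denominator" for the pandemic period, but it introduces them, with Table 10-5, for calculating EAIR and EAER only.

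On timing, SAP 8.5 says that "the onset of the pandemic was subsequent to all subjects completing Week 48". In SAP 5.1, "a subject will be considered to have completed the study if they attended Visit 13 [Week 104" (bracket closes after the number), and treatment is complete with the Week 100 dose.

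**The concern.** The two columns are calendar windows, and each subject spends a different length of time in each. A raw percentage then largely measures how long subjects could have withdrawn in that window. Because everyone had at least 48 weeks behind them on the cut date, the Prior window is the longer one for most possible entry dates.

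The denominator adds to this. Under the general rule it is the full Safety Set in both columns, so subjects who had already withdrawn or completed still count as if they could withdraw during the pandemic.

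At stake is the reading of the secondary safety variable on a question that the SAP says it will investigate. The table could show fewer withdrawals during the pandemic when the risk had not changed, or could mask a real rise.

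**Working it through.** **Inputs.** Last dose at Week 100; study complete at Week 104; maximum duration 120 weeks (Protocol 5.1.2); at-risk tail of 140 days (SAP Table 10-2); every subject past Week 48 by the pandemic (SAP 8.5, taking 11 March 2020 from SAP 10.2.4 as its onset). Let w be a subject's study week on that date. Entry dates are not in the documents. The final protocol is dated 15 May 2017, so w cannot exceed about 147.

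**The plan's own figure.** 140 days / 7 = 20 weeks, and Week 100 + 20 = 120 weeks, which matches. The tail therefore runs 120 - 104 = 16 weeks past Week 104.

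**Time in which withdrawal is possible.** Prior = min(w,104) weeks; During = max(0,104-w) weeks. For withdrawal of drug alone the limit is Week 100, which shortens the During window further.

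**Percentages with no change in risk.** Assume a constant hazard of 5 per 100 patient-years, h = 0.05/52.18 per week, and the Safety Set as denominator:

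- Prior = 1 - exp(-h·min(w,104))
- During = exp(-h·min(w,104)) - exp(-104h)

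| w | Weeks Prior / During | Prior | During |
|---|---|---|---|
| 48 | 48 / 56 | 4.5% | 5.0% |
| 60 | 60 / 44 | 5.6% | 3.9% |
| 76 | 76 / 28 | 7.0% | 2.5% |
| 90 | 90 / 14 | 8.3% | 1.2% |
| 104 | 104 / 0 | 9.5% | 0.0% |

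For example, at w=60: exp(-60h) = 0.944 and exp(-104h) = 0.905, so Prior = 5.6% and During = 3.9%.

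**Break-even.** The columns are equal at w = 51.5, 50.7 and 49.4 for assumed hazards of 2, 5 and 10 per 100 patient-years. Below that week During is slightly higher; above it During is lower.

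**Mixed entry.** With w uniform over an assumed range and hazard 5, Prior vs During is 5.0% vs 4.4% (48 to 60), 5.8% vs 3.7% (48 to 76), 7.0% vs 2.5% (48 to 104) and 7.6% vs 1.9% (48 to 120).

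**Would EAIR on Table 10-5 time be enough?** That time runs to Week 120 for a completer. With no change in risk, the During/Prior rate ratio for w up to 104 is about (104-w)/(120-w), because Prior time is all withdrawal-possible:

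- w=48: 56/72 = 0.78
- w=76: 28/44 = 0.64
- w=90: 14/30 = 0.47

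If person-time stops at withdrawal or Week 104, the ratio is 1.0 for every w below 104.

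**The case against.** Four points can be made for the plan.

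- The main withdrawal tables in SAP 10.2 also lack EAIR, so the format is consistent. That is true, but their columns are treatment groups on the same visit schedule. Here the columns differ in length by design.
- Other outputs help. All AE listings flag onset relative to the pandemic, and AEs leading to study discontinuation are listed. A dedicated eCRF page (SAP 12.6, summarized under SAP 5.1.1) records drug discontinuation and study termination with their relationship to COVID-19. These give individual context but no rate by period.
- The tables are descriptive and small. With at most 200 subjects, 5.6% vs 3.9% is about 11 vs 8 subjects (0.056 × 200 and 0.039 × 200). This stands as a limit on the harm. At w=76 the same arithmetic gives 14 vs 5.
- Completion at Week 104 is a disposition rule. An event in follow-up, a fatal one for instance, might still be recorded as leading to study discontinuation. This also stands: withdrawal after Week 104 is essentially, not strictly, impossible, and a shortened time at risk needs a matching event rule.

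A reader might also infer that follow-up after Week 104 dilutes the planned During percentages. The documents do not support this. Person-time does not enter a raw percentage, and the rule that keeps off-drug subjects in the During denominator is stated for EAIR and EAER. That follow-up matters only if EAIR is added on Table 10-5 time.

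**Conclusion.** The concern holds. As written, the two withdrawal tables have no exposure adjustment and no period denominator, and they compare windows that are about equal only for subjects near Weeks 48 to 52 on 11 March 2020. For later weeks the During percentage is lower with no change in risk, by 1.7 percentage points at w=60 (5.6 - 3.9) and 4.5 at w=76 (7.0 - 2.5). These sizes rest on an assumed constant hazard of 5 per 100 patient-years, the Safety Set denominator and assumed values of w.

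Two stronger readings go too far. The direction is not fixed: at w=48 During is slightly higher. Nor can it be said that post-Week-104 time falls almost wholly in the During column. That share is 100% if everyone was at or before Week 104, but 89%, 65% and 55% for w uniform over 48 to 120, 48 to 147 and 90 to 130, and the documents give no entry dates.

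The main safety tables are unaffected.

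**What to change.** In SAP 10.2.4, for the two withdrawal tables only:

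1. Add EAIR with 95% CI for each period. Start the During clock on 11 March 2020; SAP 10.2.2 otherwise counts time at onset from the first dose.
2. State the percentage denominator for each period as subjects still on study at its start. This alone does not equalize the windows: at w=60 it gives 5.6% vs 4.1%, so the percentages should be read with the rates.
3. End time at risk at the earliest of study discontinuation, Week 104 and last dose + 28 days, which is the end of the dosing period in SAP 3.2.2. Do not use the 140-day tail here.
4. Count in the rate only events with onset inside that time, and list any flagged event with later onset separately.

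Add a footnote that events are placed by onset date, so an event starting before 11 March 2020 that leads to withdrawal afterwards counts as Prior. Keep Table 10-5 for the other tables.

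The cost is SAP wording and one derived time-at-risk variable, with no new data. The small downside is a second time-at-risk definition that needs a footnote.

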**Table 10-5: Calculation of exposure time at risk in relation to COVID-19**

Study Period	Start Date	End Date	Duration of Exposure
Prior to COVID-19 pandemic	First dose of BKZ 160mg in PA0009	10MAR2020	
For subjects who did not discontinue medication in the ‘Prior to COVID-19 pandemic’ phase (ie, where the last dose of BKZ 160mg is on or after 11MAR2020): (End date – start date + 1)
 
For subjects who discontinued medication in the ‘Prior to COVID-19 pandemic’ phase (ie, where the last dose of BKZ 160mg is prior to 11MAR2020): If the following is true: Minimum of (Last dose date in PA0009 + 140a) and (Date of last clinical contactb) is <math>\geq</math>11MAR2020 Then the duration of exposure will be calculated as follows: (End date – start date + 1) Else duration of exposure will be calculated as follows: Minimum of (Last dose date in PA0009 – First dose date in PA0009 + 140a) and (Date of last clinical contactb – First dose date in PA0009 + 1) For subjects that died on or before 10MAR2020: Date of death – Start date + 1 Note: If the date of death is later than 140 days following the last dose of BKZ, this rule does not apply.

**Table 10-5: Calculation of exposure time at risk in relation to COVID-19**

Study Period	Start Date	End Date	Duration of Exposure
During the COVID-19 pandemic	11MAR2020	Last dose of BKZ 160mg in PA0009	
For subjects who did not discontinue medication in the ‘Prior to COVID-19 pandemic’ phase (ie, where the last dose of BKZ 160mg is on or after 11MAR2020):
 
Minimum of (Last dose date in PA0009 – 11MAR2020 + 140a) and (Date of last clinical contactb – 11MAR2020 + 1)
 
For subjects that died: Date of death – 11MAR2020 + 1.
 
Note: If the date of death is later than 140 days following the last dose of BKZ, this rule does not apply.
 
For subjects who discontinued medication in the ‘Prior to COVID-19 pandemic’ phase (ie, where the last dose of BKZ 160mg is prior to 11MAR2020):
 
If the following is true: Minimum of (Last dose date in PA0009 + 140a) and (Date of last clinical contactb) is <math>\geq</math>11MAR2020
 
Then the duration of exposure will be calculated as follows: [Minimum of (Last dose date in PA0009 – 11MAR2020 + 140a) and (Date of last clinical contactb – 11MAR2020 + 1)]
 
For subjects that died within 140 days following the last dose of BKZ this rule be adjusted to: Date of death – 11MAR2020 + 1

AE=adverse event; BKZ=bimekizumab; SFU=Safety Follow-Up.

a 140 days refer to 5 half-lives of BKZ.

b Date of last clinical contact for each subject is defined as the maximum of [last visit date including SFU visit, last AE start date (including imputed AE start dates), date of study termination or completion, last date of study drug administration following rules for partial treatment end dates as per [Section 4.2.5](#)].

### 10.3 Clinical laboratory evaluations

The routine clinical laboratory evaluations specified in [Table 10-6](#) will be summarized. If any

additional analytes are recorded, they will be listed only.

**Table 10–6: Laboratory measurements**

Hematology	Biochemistry	Urinalysis
Basophils	Calcium	Urine dipstick for pregnancy testing a
Eosinophils	Chloride	Urinalysis b
Lymphocytes	Magnesium	
Atypical lymphocytes	Potassium	
Monocytes	Sodium	
Neutrophils	Glucose (random)	
Hematocrit	BUN	
Hemoglobin	Creatinine	
MCH	AST	
MCHC	ALT	
MCV	ALP	
Platelet count	GGT	
RBC count	Total bilirubin	
WBC count	LDH	
	Total cholesterol	
	Uric acid	
	CRP	

ALP=alkaline phosphatase; ALT=alanine aminotransferase; AST=aspartate aminotransferase; BUN=blood urea nitrogen; CRP=high sensitivity C-reactive protein; GGT=gamma glutamyltransferase; LDH=lactate dehydrogenase; MCH=mean corpuscular hemoglobin; MCHC=mean corpuscular hemoglobin concentration; MCV=mean corpuscular volume

a A urine pregnancy test will be performed for women of childbearing potential if there is a suspicion of pregnancy. A positive urine pregnancy test should always be confirmed with a serum pregnancy test.

b These measurements will be performed only if a urinalysis is required for safety reasons.

Separate summary tables for hematology and biochemistry variables will be provided, based on data from scheduled visits. Observed values and changes from PA0009 Laboratory Baseline will be summarized, by treatment group at completion of PA0008 and overall. CRP will be summarized separately as described in [Section 8.3](#).

Any laboratory values (with the exception of CRP) reported as <xx or >xx in the database will be imputed as the value of 'xx' for the purpose of calculating changes from baseline and for summary statistics. The original value will be reported in any listings.

Summary tables of the number and percentage of subjects experiencing at least 1 on-treatment markedly abnormal value during the Treatment Period (excluding any measurements that occurred prior to the first administration of study medication in PA0009 or more than 140 days after the last administration of study medication) for each hematology and biochemistry variable will be presented by treatment group at completion of PA0008 and overall. Markedly abnormal values for hematology and biochemistry are defined in [Table 10-7](#) and [Table 10-8](#).

Tables of markedly abnormal laboratory data subject numbers will be provided including all values classified as markedly abnormal at scheduled and unscheduled visits.

